2.3.2 Secondary endpoints

- Status on an ordinal scale assessed daily while hospitalized and on days 15 and 28 in IP versus control group patients
- NEWS assessed days 3, 5, 8, 11 while hospitalized and on days 15 and 29 in IP versus control group patients
- Rate of mechanical ventilation in IP versus control group patients
- Duration of mechanical ventilation (if applicable) in IP versus control group patients
- Duration of supplemental oxygen in IP versus control group patients
- Time to return to SpO₂ > 94% on room air
- Duration in ICU (if applicable) in IP versus control group patients
- Rate of Mortality in IP versus control group patients
- Duration of hospitalization in IP versus control group patients
- Time to discharge in IP versus control group patients
- Effect on the rate of change of partial pressure of oxygen (PaO₂) and PaO₂/FiO₂ ratio taken at baseline and measured once daily up to 2 weeks of treatment in IP versus control group patients

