11.3 Secondary Efficacy Analysis: Time to Event General Considerations

Time to event endpoints will not be evaluated if any subjects experienced an event prior to randomization in any of the treatment arms.

Time-to-event endpoints without competing risk will be analysed for each dosing group using the Kaplan-Meier (KM) method. Medians (with corresponding 95% confidence intervals) and quartiles (25th and 75th percentiles), minimum, and maximum survival times will be presented. In addition, the number of patients with an event and the number of censored patients will also be reported. The corresponding Kaplan-Meier survival plot will also be presented along with number at risk statistics at the appropriate time points. Adjusted hazard ratio, 95% CIs and p-values between active treatment groups to SOC under Cox proportional hazard model with age, site and treatment groups as covariates will be reported.

Time-to-event endpoints with competing risk will be analysed for each dosing group using the Cumulative Incidence Function-CIF (KM) graphical display. Adjusted hazard ratio, 95% CIs and p-values between active treatment groups to SOC under Fine-Gray sub-distribution hazard model with age, site and treatment groups as covariates will be reported. Competing risk is identified by the presence of death outcome, which prevent the observation of the current outcome of interest.

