11.6 Secondary Efficacy Analysis: Respiratory Support

For the part of the analysis, respiratory support is defined as:

- Any respiratory support (any of Oxygenation only, Mechanical Ventilation (Invasive and non invasive), ECMO)
- Oxygenation only
- Invasive Mechanical Ventilation
- Non Invasive Mechanical Ventilation
- ECMO

11.6.1 Rate of Respiratory Support: Oxygenation only, Mechanical Ventilation (Invasive and non invasive), ECMO

Counts and percentages of patients for respiratory support at least once will be reported for each treatment arm. If patients were eligible for respiratory support but did not receive one due to lack of resources, an additional analysis on counts and percentages of patients required to receive respiratory support will be reported for each treatment arm. Separate 95% CIs (Newcombe) and p-values (Chi-Squared test without continuity correction) will be computed between SOC and treatment arms A and B for patients with at least one respiratory support.

11.6.2 Duration of Respiratory Support: Oxygenation only, Mechanical Ventilation (Invasive and non invasive), ECMO

Counts and percentages of patients with the following categories (based on total number of hours of respiratory support) will be reported for each type of respiratory support and for each treatment arm. The duration calculation is only applicable to patient with respiratory support. For patients with ongoing respiratory support with no end date and time at data cut off, the date of data cut off will be used to calculate the end date for the ongoing at time of data cut off category.

The duration is defined as:

Date and time at end of respiratory support-Date and time at end of respiratory support.

- < 6 hours
- \geq 6 hours but < 12 hours
- \geq 12 hours but < 24 hours
- \geq 24 hours but < 72 hours
- \geq 72 hours but < 120 hours
- > 120 hours
- Ongoing at time of data cut off (\geq 6 hours) [The hour can be amended based on real data]
- Ongoing at time of data cut off (\geq 12 hours) [The hour can be amended based on real data]
- Ongoing at time of data cut off (\geq XX hours) etc...
- Prolonged respiratory support (consecutive respiratory support for 21 days with at least \geq 6 hours per day)

Separate 95% CIs (Newcombe) and p-values (Chi-Squared test without continuity correction) will be computed between SOC and treatment arms A and B for prolonged respiratory support.

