11.6.3 Time to Respiratory Support: Oxygenation only, Mechanical Ventilation (Invasive and non invasive), ECMO

The time to respiratory support (Day) is defined as:

Date of first respiratory support – Date of Baseline Assessment + 1.

If the patient did not require respiratory support, the patient will be censored at the last known date the patient is known to not require respiratory support:

Final Date of Confirmation of no respiratory support needed - Date of Baseline Assessment + 1.

If a patient died before obtaining respirator support, the patient will be censored as a competing risk based on the following:

Date of Death - Date of Baseline Assessment + 1.

11.6.4 Time from first Oxygenation Support to first termination of Oxygenation Support:

This calculation is only applicable for those with oxygenation support.

The time to from first oxygenation support to first termination of oxygenation support is defined as:

Date of first termination of oxygenation support – Date of first oxygenation support + 1.

If the patient was still on oxygenation support, the patient will be censored at the last known date the patient is known to still on oxygenation support:

Final date of confirmation of still on oxygenation support - Date of first oxygenation support + 1.

If a patient died before terminating oxygenation support, the patient will be censored as a competing risk based on the following:

Date of Death - Date of Baseline Assessment + 1.

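### SAP 11.6.4 does not say how escalation is handled, so a move from oxygen to ventilation or ECMO can be coded as coming off oxygen

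*SAP*

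**What the plan says.** SAP 11.6.4 covers patients who received oxygenation support. The rule begins "The time to from first oxygenation support to first termination of oxygenation support is defined as", and the event time that follows is "Date of first termination of oxygenation support – Date of first oxygenation support + 1". For censoring, "If the patient was still on oxygenation support, the patient will be censored at the last known date" of confirmed support. For death, "If a patient died before terminating oxygenation support, the patient will be censored as a competing risk based on the following", and the time given there runs from the baseline assessment.

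The general rule in SAP 11.3 also names death alone: "Competing risk is identified by the presence of death outcome, which prevent the observation of the current outcome of interest". That section specifies a Fine-Gray sub-distribution hazard ratio for each active arm against SOC where a competing risk exists.

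The opening list of SAP 11.6 has an umbrella category, "Any respiratory support (any of Oxygenation only, Mechanical Ventilation (Invasive and non invasive), ECMO", followed by separate entries for oxygen alone, invasive ventilation, non-invasive ventilation and ECMO. Section 11.6.4 uses neither the umbrella term nor the oxygen-alone label; it says only oxygenation support.

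Among the secondary endpoints in SAP 2.3.2 is "Duration of supplemental oxygen in IP versus control group patients". The SAP does not map that endpoint to a section, but 11.6.4 is the only place that yields a between-arm hazard ratio for time on oxygen.

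**The concern.** For this endpoint a higher hazard reads as benefit, so it matters which ways of stopping oxygen count. Take a patient on nasal oxygen who starts NIV on Day 3 and is intubated on Day 5. If oxygen alone is the state being followed, that state ends on Day 3. The rule has no censoring or competing-event category to catch the move, so the patient can be scored with a favourable event on Day 3. Because the rule takes the first termination, a trial off oxygen that fails the same day can also be a permanent success.

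Escalation is to be expected. Protocol 5.1 admits patients on oxygen, NIV or high flow (WHO score 4 or 5). Protocol 5.4.2 keeps patients who progress to mechanical ventilation in the study. New ventilation is itself part of a secondary objective. Phase 2b is open label, so those who decide on oxygen and ventilation know the arm.

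Protocol 4.1 and SAP 2.1 say that Phase 2b data will be used to select and rank the secondary endpoints for Phase 3. An endpoint whose estimate is pulled the wrong way could mislead that choice.

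**Working it through.** **Text check.** The documents state no sample size, event count or rate for this analysis, so there is no plan figure to reproduce. The rules side by side:

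| Patient's course | Rule in SAP 11.6.4 or 11.3 |
|---|---|
| Comes off oxygen, breathing room air | Event |
| Still on oxygenation support | Censored |
| Dies before termination | Competing event |
| Moves to NIV, invasive ventilation or ECMO | None stated |
| Off oxygen briefly, then back on | Event at the first stop; no rule for the return |

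**Illustration 1 (all rates assumed).** Weaning hazard w = ln 2 / 7 = 0.0990 per day in both arms. Escalation hazard e = 0.02 (better arm) or 0.04 (worse arm). Escalated patients stay on support at least 10 more days. Death is left out.

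Escalation coded as termination, by Day 7: 1 − exp[−7(w + e)].
- Better arm: 1 − exp(−7 × 0.1190) = 56.5%; median ln 2 / 0.1190 = 5.8 days.
- Worse arm: 1 − exp(−7 × 0.1390) = 62.2%; median 5.0 days.

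True removal of all support, by Day 7: [w/(w + e)] × {1 − exp[−7(w + e)]}.
- Better arm: (0.0990/0.1190) × 0.565 = 47.0%; median 7.7 days.
- Worse arm: (0.0990/0.1390) × 0.622 = 44.3%; median 8.7 days.

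The direction is reversed.

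**When does it reverse?** With escalation coded as termination the event hazard is w + e. The worse arm looks better only if its extra escalation hazard exceeds its loss of weaning hazard. Here break-even is 0.02 / 0.0990 = 20% slower weaning.

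| Weaning in worse arm | Coded as termination, worse vs better | True removal, worse vs better |
|---|---|---|
| Same | 62.2% vs 56.5% | 44.3% vs 47.0% |
| 20% slower | 56.6% vs 56.5% | 37.6% vs 47.0% |
| 30% slower | 53.5% vs 56.5% | 33.9% vs 47.0% |

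The true-removal entries use the same formula; at 20% slower, (0.0792/0.1192) × 0.566 = 37.6%. So a reversal is conditional, but the pull toward the worse arm is present in every row.

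**Illustration 2 (all rates assumed; the planned effect measure).** Daily hazards in the reference arm: weaning 0.08, escalation 0.01, death 0.003, over 28 days. Sub-distribution hazard ratios (worse vs reference arm) come from simulation with 20,000 patients per arm and complete follow-up. A value above 1 means that the worse arm looks better.

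| Worse arm | Escalation = termination | Escalation = competing event |
|---|---|---|
| Escalation ×2, same weaning | 1.10 | 0.87 |
| Escalation ×3, same weaning | 1.22 | 0.78 |
| Escalation ×3, weaning 10% slower | 1.13 | 0.72 |
| Escalation ×3, weaning 15% slower | 1.08 | 0.68 |
| Equal rates | 1.00 | 1.00 |

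For the first row, 28-day incidence is 91.7% (worse) against 89.6% when escalation counts, and 73.3% against 79.7% when it does not. In the tripled case break-even is 0.02 / 0.08 = 25% slower weaning.

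**Time origin.** Event and censoring times run from first oxygen; death time runs from baseline. As an example, a patient starts oxygen 4 days before baseline and dies 6 days after it. The death time is 6 + 1 = 7 under the SAP, but 10 + 1 = 11 on the clock used for events. Patients enter already on oxygen or NIV/high flow, so first oxygen can precede randomization. There is a further consequence: SAP 11.3 drops a time-to-event endpoint if any patient had the event before randomization. If escalation is a termination, one patient who went from oxygen to NIV before randomization would remove the whole analysis.

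**The case against.** The strongest reply is that oxygenation support may mean any support that delivers oxygen. Protocol 7.3.2 and 7.4.4 record oxygen requirement as its own item, and a ventilated patient may still be recorded as requiring it. Such a patient would be censored as still on support, and escalation would not be an event. The eCRF and mock shells that might settle this are not available. This stands against any flat statement that escalation will be scored as success. It does not remove the point: SAP 11.6 already has an umbrella term for any support and 11.6.4 does not use it, so two programmers could code opposite results.

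A reader might infer that the result will be reversed. The documents do not support that. The rates are assumed, and moderately slower weaning in the worse arm cancels the reversal. The first illustration also leaves 28% and 33% of patients on support at Day 15, whereas Table 2 (the Phase 3 planning distribution) puts 5 + 2 + 1 = 8% of SOC patients in categories 4 to 6. Its figures therefore show direction and not expected size. Its implied hazard ratio is 0.1390/0.1190 = 1.17. With about 90 events over two arms of about 50, the standard error of the log ratio is √(4/90) = 0.21 and the 95% interval about 0.77 to 1.77, so a bias of that size would sit inside sampling noise.

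A reader might also infer that the duration analysis in 11.6.2 fails in the same way. Escalation does shorten the oxygen-alone duration there. But duration of any respiratory support is reported beside it, and the only between-arm test in that section is for prolonged support.

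Finally, this is one secondary analysis in a phase that SAP 11.1 describes as exploratory. The WHO-7 analysis, ventilation rate, time to SpO2 above 94% on room air, and mortality would all show deterioration. That stands and limits the weight of the point.

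**Conclusion.** The concern holds as an undefined event rule. Section 11.6.4 omits escalation and failed trials off oxygen, no other section supplies a rule, and the category list in 11.6 makes the unfavourable coding a natural one. Under that coding the comparison is biased toward the arm that escalates more. It can reverse when weaning rates are similar: hazard ratios of 1.08 to 1.22 in favour of the worse arm, against 0.68 to 0.87 with escalation as a competing event, all under assumed constant rates. Neither that coding nor a reversal is established by the documents. The mixed time origin is a separate defect in the same section and holds on either reading. The consequence is confined to this secondary analysis and to any use of it in choosing Phase 3 endpoints. It should be corrected before the analysis is programmed.

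**What to change.** In SAP 11.6.4:

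1. Define termination as the first date on which the patient is alive and receives none of supplemental oxygen, high-flow/NIV, invasive ventilation or ECMO. Require confirmation at the next recorded assessment, by the support start and stop records, or at discharge without oxygen.
2. State that escalation is never a termination. In the main analysis treat it as continuing support; as a sensitivity analysis treat it as a competing event.
3. Keep death as a competing event, and measure event, censoring and death times from one origin (randomization/baseline).

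The cost is SAP wording and derivation, with no new procedure. Fewer events will be counted. The main version measures time to freedom from all support, which is somewhat broader than supplemental oxygen alone, and the text should say so. Scheduled daily status covers Days 2 to 14 in hospital only (Protocol 7.3.2 and Table 3). Later dates will therefore rest on the support start and stop times that 11.6.2 presupposes, or on the Day 15 and Day 29 visits.

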### 5.1 Inclusion Criteria

1. Male and female subjects aged  $\geq 18$  years of age
2. Confirmed coronavirus infection
  - a) Positive real-time fluorescence polymerase chain reaction of the patient's respiratory or blood specimens for SARS-CoV-2 nucleic acid
  - b) Viral gene sequences in respiratory or blood specimens that are highly homologous to SARS-CoV-2
  - c) Any other diagnostic test accepted by local regulatory authorities
3. Must be hospitalized and requiring supplemental oxygen, or on non-invasive ventilation or high flow oxygen devices (Score of 4 or 5 on WHO Ordinal Clinical Scale)
4. Female subjects of childbearing potential who are sexually active with a non-sterilized male partner must use at least 1 highly effective method of contraception (e.g. oral contraceptives, intrauterine device, diaphragm plus spermicide) from the time of screening and must agree to continue using such precautions for 90 days after the final dose of study drug(s)

5. Non-sterilized males who are sexually active with a female partner of childbearing potential must use condom plus spermicide from day 1 through 90 days after receipt of the last dose of study drug(s)
6. Subjects (or legal designate) must have the capacity to understand, sign and date a written, informed consent form and any required authorization prior to initiation of any study procedures

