## 7.3 Visits

### 7.3.1 Visit 1 (Screening/Baseline/Enrollment)

At Visit 1, information will be collected for evaluation of trial eligibility by provided information as follows and patients will be randomized and dosed after confirmation of eligibility:

- Signing ICF (prior to any trial-related activities)
- Inclusion criteria and exclusion criteria
- Demographics (gender, date of birth, race and ethnic origin) and relevant medical and surgical history
- Confirmation of COVID-19 diagnosis (SARS-CoV-2 RNA confirmation). Include dates of onset of symptoms (if available) and initiation of treatment.
- Pregnancy test (females of reproductive age; Romania: Serum beta-human chorionic gonadotropin [ $\beta$ -HCG]; Rest of World: Serum beta-human chorionic gonadotropin [ $\beta$ -HCG] or urine test is acceptable)
- Vital signs measurements (including pulse, respiration rate, body temperature, systolic and diastolic blood pressure measured with the patient in a seated position [if possible] after  $\geq 3$  minutes of rest), and SpO2. Body weight and height will be included for the screening visit only
- Limited Physical Exam
- Assess baseline measures of clinical support
  - Hospitalized
  - Oxygen requirement
  - Non-invasive mechanical ventilation (via mask)
  - Mechanical ventilator requirement (via endotracheal tube or tracheostomy tube)
  - ECMO requirement
  - Ordinal Scale Assessment
    1. Not hospitalized, no limitations on activities
    2. Not hospitalized, limitation on activities
    3. Hospitalized, not requiring supplemental oxygen
    4. Hospitalized, requiring supplemental oxygen
    5. Hospitalized, on non-invasive ventilation or high flow oxygen devices
    6. Hospitalized, on invasive mechanical ventilation or ECMO
    7. Death
  - For the purposes of eligibility/baseline the worse score from the previous day (Day -1) will be used
  - NEW Score
- Safety laboratory testing
- Child-Pugh Score
- Cytokine Markers
- PaO2 and PaO2/FiO2 ratio
- ECG
- VAS (if possible)
- Extent of Dyspnea (if possible). For the first questionnaire (at baseline), the patient compares their current shortness of breath to their shortness of breath when they are well.)
- Concomitant medications documented
- Randomization\* after eligibility confirmation. All screening/baseline procedures must be completed prior to randomization and administration of study medication.

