#### **7.4.9 Prior and Concomitant Therapies**

All medications (prescription and non-prescription), treatments, and therapies taken by the patient from screening throughout their entire participation in the study, including those initiated prior to the start of the study, must be recorded on the patient's source document and on the appropriate page of the eCRF. The dose, unit, frequency, route, indication, date the medication was started, and date the medication was stopped (if not ongoing) must be recorded.

All Investigational COVID-19 therapeutic agents used both prior to, and current to randomization and participation in the study should be captured in the CRF.

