11.8.2 Time to Hospitalization and ICU discharge

The time to discharge is defined as:

Date of discharge from hospital – Date of Baseline Assessment + 1. (For hospitalization)

Date of discharge from ICU – Date of Baseline Assessment + 1. (For ICU)

If the patient did not discharge from hospital or ICU patient will be censored at the last known date the patient is known to be still in hospital/ICU according to the following:

Final Date of Confirmation the patient is still in hospital - Date of Baseline Assessment + 1. (For hospitalization)

Final Date of Confirmation the patient is still in ICU - Date of Baseline Assessment + 1. (For ICU)

If a patient died discharge, the patient will be censored as a competing risk based on the following:

Date of Death - Date of Baseline Assessment + 1.

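### SAP 11.6.4 times oxygen duration from first oxygen support, which normally precedes randomisation; power is lost if prior oxygen time varies between patients

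*SAP*

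**What the plan says.** SAP 11.6.4 opens its definition with "The time to from first oxygenation support to first termination of oxygenation support is defined as" and has three time formulas, on two origins:

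- Event: "Date of first termination of oxygenation support – Date of first oxygenation support + 1".
- Censoring: "Final date of confirmation of still on oxygenation support - Date of first oxygenation support + 1".
- Death as a competing risk: "Date of Death - Date of Baseline Assessment + 1".

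Nothing limits first oxygen support, or its first termination, to dates after randomisation.

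Protocol 5.1, item 3, sets the entry state: "Must be hospitalized and requiring supplemental oxygen, or on non-invasive ventilation or high flow oxygen devices". Protocol 7.3.1 sets the day on which it is judged: "For the purposes of eligibility/baseline the worse score from the previous day (Day -1) will be used". Protocol 7.4.9 has treatments and therapies recorded with start dates, "including those initiated prior to the start of the study", so a pre-trial oxygen start can reach the database.

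SAP 11.3 assigns a Fine-Gray model with age, site and treatment to endpoints with death as a competing risk. It mentions neither delayed entry nor adjustment for earlier oxygen time. It also says that a time-to-event endpoint is not evaluated at all if any patient had the event before randomisation.

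The other time-to-event analyses (SAP 11.4.1, 11.5.1, 11.6.3, 11.7.2 to 11.7.4, 11.8.2 and 11.9) count from the Baseline Assessment. For discharge, for example, the origin is "Date of Baseline Assessment + 1. (For hospitalization").

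**The concern.** Treatment can act only after randomisation. When the clock starts earlier, each observed time is the sum of a lead (days on oxygen before randomisation) and the time that treatment could shorten. Without delayed entry, the risk set at a given day since first oxygen mixes patients at different points after randomisation, including some who had not yet been randomised when they reached that day. If leads differ between patients, they add noise to the ordering on which the hazard ratio depends.

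Duration of supplemental oxygen is a listed secondary endpoint (SAP 2.3.2), and 11.6.4 is its only between-arm time-to-event analysis. SAP 11.6.2 tests only prolonged respiratory support, defined as 21 consecutive days. Protocol 4.1 and SAP 2.1 say that Phase 2b data will be used to select and rank secondary endpoints for Phase 3, so an attenuated result could push this one down the list for a reason unrelated to the drug.

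**Working it through.** **The plan's own figure.** No power is stated for oxygen duration. The only powered figure is the Phase 3 sample size for the ordinal primary endpoint. It reproduces, and the point does not depend on it. With the average proportions p from Table 2, N = 12(1.960 + 1.282)² / [0.5596² × (1 − Σp³)], where Σp³ = 0.126. This gives 460.9 against the stated 462, and 462/0.9 gives 514 after rounding up.

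**The time scales.** Let a patient start oxygen L days before baseline.

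- Oxygen stopped d days after baseline: 11.6.4 records d + L + 1.
- Still on oxygen d days after baseline: it records d + L + 1.
- Death d days after baseline: it records d + 1.

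So leads enter the event and censoring times but not the death times. On a duration scale, assumed stays after randomisation of 5 and 8 days (ratio 5/8 = 0.63) become 8 and 11 (0.73) with L = 3, and 10 and 13 (0.77) with L = 5. The 3-day difference is unchanged.

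**Cox simulation.** From the plan: 50 per arm (SAP 2.5), two-sided 5% (Protocol 10.9.2), follow-up to Day 29, and 90% of SOC patients off oxygen by Day 15 (Table 2 puts 5 + 2 + 1 + 2 = 10% in categories 4 to 7). An exponential time then has daily rate −ln(0.10)/15 = 0.154, a median of 4.5 days. Assumed: a true hazard ratio of 1.6 and the distribution of leads. The same simulated patients were analysed on both clocks, in whole days. The SAP does not say how ties are handled, so both usual methods are shown.

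| Lead before randomisation | Power, Efron ties: baseline clock → first-oxygen clock | Power, Breslow ties: baseline clock → first-oxygen clock |
|---|---|---|
| Constant 3 days | no change | no change (53% on both) |
| Uniform 0 to 3 days | 63% → 63% | not run |
| Exponential, mean 3 days | 63% → 50% | 55% → 44% |
| Exponential, mean 5 days | 64% → 40% | 55% → 32% |

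An exponential lead of mean 1 day cost almost nothing. With Breslow ties the mean hazard ratio fell from 1.53 to 1.46 (mean 3 days) and 1.37 (mean 5 days). A less variable lead (gamma, shape 2, Breslow) cost less: 57% fell to 52% at mean 3 days and to 44% at mean 5 days.

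**Simulation with deaths handled as in Fine-Gray.** Here 2% of patients die and stay in the risk set, and follow-up is 28 days. Assumed: an SOC median of 5 or 8 days and exponential leads.

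| True HR | SOC median | Mean lead 3 days: power, baseline → first-oxygen clock | Mean lead 5 days: power, baseline → first-oxygen clock |
|---|---|---|---|
| 1.5 | 5 days | 40% → 33% | 41% → 26% |
| 1.5 | 8 days | 43% → 40% | 41% → 33% |
| 1.75 | 5 days | 62% → 53% | 62% → 38% |
| 1.75 | 8 days | 67% → 62% | 68% → 55% |

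A mean lead of 1 day cost about 1 point (41% to 40% at hazard ratio 1.5, median 5 days), and a constant 3 days changed nothing. With a true hazard ratio of 1.0, rejection was about 4 to 6% on either clock. These runs kept deaths in the risk set on both clocks, so they do not measure any effect of the mixed death origin.

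**The case against.** **First oxygen may mean first on study.** The term is undefined. SAP 11.6.3 counts from baseline to first respiratory support in patients who are nearly all on support already, which works only if first means first on study. Read that way, the 11.6.4 clock starts at about Day 1 and the problem largely disappears. The ambiguity is real, but 11.6.4 does not say this. Elsewhere the SAP does mark the distinction: section 10 defines one COVID-19 treatment exposure from randomisation and a separate overall one.

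**Total duration may be what is wanted.** SAP 11.8.1 likewise counts hospital stay from admission. That is a legitimate description, but 11.8.1 reports only counts and percentages, and the between-arm analysis of discharge, 11.8.2, starts at baseline. The same division would suit oxygen.

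**The stakes are modest.** This is an unpowered secondary analysis in a stage that SAP 11.1 calls essentially exploratory, and time to SpO₂ above 94% on room air (11.7.2) already runs from baseline. Both points stand and limit the weight of the finding. The room-air endpoint is only a partial substitute.

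**Stronger readings that the documents do not support.** A reader might infer that every patient carries guaranteed event-free time because anyone already off oxygen would be ineligible. The previous-day scoring rule allows a patient who is off oxygen at randomisation to qualify, and a patient who had stopped and restarted could also enter. A reader might also infer that the hazard ratio is always attenuated. It is not: a constant lead leaves it unchanged. Nor is this a false-positive problem, because randomisation balances leads in expectation.

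**Conclusion.** The point holds, with a condition. As written, 11.6.4 starts the event and censoring clocks at a date that normally precedes randomisation, times deaths from a different date, and has no delayed entry to compensate. If leads vary between patients, the hazard ratio moves towards 1 and power falls.

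The size cannot be fixed from the documents, which give no days on oxygen before randomisation. At 50 per arm and hazard ratio 1.6 under Cox, the range runs from no loss (constant lead), through almost none (about 1 day), to roughly 10 to 15 points (exponential, mean 3 days) and 20 to 30 points (exponential, mean 5 days). With deaths handled as in Fine-Gray and hazard ratios of 1.5 and 1.75, the losses were 3 to 9 points at mean 3 days and 8 to 24 points at mean 5 days. The larger figures need long and highly variable leads.

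The open definition of first termination adds a separate risk. One patient whose first oxygen episode ended before randomisation could trigger the SAP 11.3 rule and remove the endpoint. The change should be made, but it does not affect the primary analysis.

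**What to change.** In SAP 11.6.4:

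1. Start the event, censoring and death times at the Baseline Assessment (randomisation), so that all three share one scale.
2. Restrict the analysis to patients on oxygen support at baseline, and state whether high flow and non-invasive ventilation count as oxygen support here.
3. Define the event as the first termination of oxygen support after baseline. Moving the origin alone is not enough: a termination before randomisation would give a zero or negative time or invoke the 11.3 rule.
4. Report days on oxygen before randomisation as a baseline characteristic. Total oxygen duration, including pre-trial days, can still be reported descriptively.

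The cost is SAP wording. The data and the model stay the same.
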